Use of a Red-Rubber Catheter to Facilitate Nasotracheal Intubation in Adult Patients: A Prospective Randomized Controlled Trial

NCT number: NCT03779984

Protocol Date: 02/14/2022

English ICF date: 05/09/2022

**The University of Texas Southwestern Medical Center at Dallas
Institutional Review Board**

Protocol

Use of a Red-Rubber Catheter to Facilitate Nasotracheal Intubation in Adult Patients: A Prospective Randomized Controlled Trial

Institution/Funding Source: Department of Anesthesia and Pain Management – University of Texas Southwestern Medical Center

1. Introduction and Purpose:

Nasotracheal intubation is used to facilitate oropharyngeal surgery in many patients, however, epistaxis is a common complication (1). Several methods to reduce epistaxis during nasotracheal intubation have been studied in adults and children. The use of a red-rubber catheter is effective in guiding nasotracheal intubation in children, however it has not been studied in adults in a prospective, randomized, controlled trial. This study was designed to compare the effectiveness of using a red-rubber catheter versus standard, direct insertion of a thermosoftened, lubricated nasal endotracheal tube into the naris to facilitate nasotracheal intubation in adults undergoing ENT, plastics or OMFS surgery. This study will assess if the red-rubber catheter method leads to lower incidence and severity of epistaxis, and faster time to intubation compared to the current standard of care.

Hypothesis 1 – The red-rubber catheter group will have significantly lower incidence of epistaxis compared to the standard insertion group in patients undergoing nasotracheal intubation.

Primary objective: To compare the incidence of bleeding after nasotracheal intubation.

Hypothesis 2 – The red-rubber catheter group will have significantly lower severity of epistaxis compared to the standard insertion group in patients undergoing nasotracheal intubation.

Secondary objective 1: To compare the severity of epistaxis after nasotracheal intubation.

Hypothesis 3 – The red-rubber catheter group will have significantly fewer airway complications compared to the standard insertion group in patients undergoing nasotracheal intubation.

Secondary objective 2: To compare the rate of complications during nasotracheal intubation.

Hypothesis 4 – The red-rubber catheter group will have significantly lower time to intubation than the standard insertion group.

Secondary objective 3: To compare the time to intubation during nasotracheal intubation.

Hypothesis 5 – The red-rubber catheter group will have significantly less pain postoperatively than the standard insertion group.

Secondary objective 4: To compare postoperative pain after nasotracheal intubation.

2. Background

Nasotracheal intubation (NTI) is commonly utilized in oropharyngeal surgeries to provide better access to the surgical field than traditional endotracheal intubation (1). NTI is also commonly used in patients with degenerative cervical spine pathology, intraoral mass lesions or structural abnormalities, and limited mouth opening (2). NTI is generally contraindicated in cases of suspected epiglottitis, midface instability, basilar skull fractures, and coagulopathy. Minor contraindications include nasal polyps, foreign bodies, recent nasal or facial surgery, and history of frequent epistaxis (1). Some complications of NTI that have been described in the literature include epistaxis, damage to a nasal turbinate or the cribriform plate, retropharyngeal dissection, and even intracranial placement of the nasotracheal tube (3-6). One of the most common complications of NTI is epistaxis, with a reported incidence of up to 86% (7).

In adults, NTI is typically performed by using phenylephrine or oxymetazoline as a vasoconstrictor, and an adequately lubricated and often, thermosoftened, nasotracheal tube (NETT). The NETT is held perpendicular to the face and inserted below the inferior turbinate with the bevel of the tube facing away from the turbinate. When the tip of the tube is seen in the oropharynx, direct laryngoscopy is used to visualize the cords and pass the tube into the trachea. Magill forceps are often used to facilitate this final step (8).

Several studies have evaluated ways to improve the way NTI is performed and minimize epistaxis. Enk et al. utilized a Wendl tube attached to the end of the NETT to guide intubation, with removal of the Wendl tube once the NETT was in the oropharynx. They found that using the Wendl tube as a “pathfinder” significantly reduced the incidence and severity of bleeding and decreased postoperative pain, although this method took longer to perform compared to insertion of the NETT without a pathfinder (9). Lim et al. used a nasogastric tube as a guide to facilitate NTI and found that with the nasogastric tube-guided method the NETT more often passed under the inferior turbinate, was associated with lower incidence and severity of epistaxis, and required fewer manipulations to place (10). Seo et al. obturated the ETT with an inflated esophageal stethoscope and thermosoftened the NETT, finding that the severity of epistaxis during NTI was lowest when using the obturated and thermosoftened NETT (7). A recent study by Vadhanan and Tripaty compared the use of a flexible bougie to guide NTI, with the bougie-guided technique having significantly less bleeding than the conventional method but taking longer to perform (11). Another study had similar findings and additionally noted that there was no difference in the first attempt and overall success rates of NTI with the bougie-guided or conventional method (12).

In children, NTI is commonly performed using a red-rubber catheter (RRC) as a guide, and its efficacy has been studied in randomized controlled trials. Watt et al. compared room temperature and warmed NETT to the RRC method in children undergoing dental surgery and found that the RRC method had lower incidence of higher severity bleeding. Although they found that the RRC method took longer, hemoglobin oxygen desaturation did not occur in the time to intubation. They

go on to discuss the mechanism by which the RRC method may reduce epistaxis, mainly by shielding the nasal mucosa from the stiff leading edge of the NETT (13). An earlier study by Elwood et al. comparing the RRC method to the thermosoftened nasotracheal tube alone reported similar results, with the RRC group having significantly less obvious bleeding. While the RRC method took longer to perform, it also took fewer attempts for successful placement (14). A recent literature review by Lera et al. on techniques for NTI in children and adults examined 15 articles, 4 of which studied the RRC method specifically. They determined that overall this technique is associated with decreased trauma to the nasopharynx, bleeding, and postoperative pain (15).

To date, there have been no randomized controlled trials that have evaluated the efficacy of using a RRC to guide NTI in adults, although there is data to support the use of the RRC method in children. In addition, in these trials the control was the direct insertion of a nasotracheal tube into the naris, which is a common practice in adult patients. We hypothesize that RRC-guided NTI will be associated with significant lower incidence and severity of epistaxis in adult patients undergoing surgery requiring nasotracheal intubation. We also hypothesize that compared to the standard technique, the RRC method will take significantly less time to perform, will be associated with less postoperative pain, and will have fewer associated complications.

3. Concise Summary of Project:

The study population for this prospective randomized controlled trial will consist of male and female adult subjects over the age of 18 having surgery requiring NTI. Consent will be obtained by study personnel. Eligible patients will be screened by study personnel up to 1 week prior to scheduled surgery. Informed consent will be obtained in the preoperative holding area. This is a multicenter study. The MD Anderson Center is other site of the study. Each study site will enroll 56 subjects. A total of 112 subjects will be randomized to either the RRC group or control group. Oxymetazoline nasal spray will be administered with 1 spray per nostril preoperatively. Premedication with glycopyrrolate 0.2 mg and benzodiazepine at discretion of provider will be given preoperatively. Subjects will then be brought into the operating room and placed on all standard ASA monitors (BP cuff, EKG, pulse oximetry). One spray of oxymetazoline per nostril will again be administered. Standard preoxygenation will be used with a face mask and 100% O₂. After induction of anesthesia, provider will confirm mask ventilation and 1 more spray of oxymetazoline will be administered per nostril. Intubation will first be attempted via a naris (13). Size 6.5 nasotracheal RAE tubes (Shiley Nasal RAE Tracheal Tube with TaperGuard Cuff, manufactured by Covidien llc, Mansfield, MA 02048) will be used in female patients and size 7.5 in males (16). The tubes will be thermosoftened by allowing them to sit in warm saline prior to use (18). Water-based lubrication will be used for dilation and intubation. Time from insertion of RRC or NETT into nasal passage to first recording of end-tidal CO₂ will be recorded. Direct video laryngoscopy will be used to facilitate placement of the nasotracheal RAE tube. Five minutes after intubation, a non-collaborating anesthesia provider blinded to the method of intubation will grade the severity of bleeding by performing direct video laryngoscopy, inspecting the posterior pharynx and using a scale described originally by Sugiyama et al (19) and again by Earle et. al (20)- no epistaxis (no blood observed on either the surface of the tube or the posterior pharyngeal wall); mild epistaxis (blood apparent on the surface of the tube or posterior pharyngeal wall); moderate epistaxis (pooling of blood on the posterior pharyngeal wall); and severe epistaxis (a large amount of blood in the pharynx impeding nasotracheal intubation—before the epistaxis assessor enters the

operating room, requiring suction for intubation or necessitating urgent orotracheal intubation.) Degree of nasal pain on the side of intubation will be rated on a numerical rating scale at 30 and 60 minutes in the post-anesthesia care unit (9).

The removal/reinsertion of the laryngoscope and endotracheal tube or switching of the laryngoscopist will be evaluated as a new intubation attempt.

The study duration starts from operating room preoperative holding area admission to discharge from the Post Anesthesia Care Unit (PACU).

RRC group: The funnel end of a RRC (Bard All-Purpose Urethral Catheter, manufactured by C. R. Bard, Inc, Covington, GA 30014 USA) will be securely attached to a room-temperature nasotracheal tube. A 20 Fr RRC will be used with the size 7.5 nasotracheal RAE tube and an 18 Fr RRC will be used with the size 6.5 nasotracheal RAE tube. The tubes will be warmed in saline prior to use (18). Water-based lubrication will be applied to the RRC. The rounded end of the catheter will be introduced into a naris and advanced to the posterior oropharynx and visualized with a laryngoscope. The catheter will then be removed from the end of the nasotracheal tube and withdrawn through the mouth. The nasotracheal tube will then be guided into the trachea past the vocal cords under direct visualization with CMAC video laryngoscope MAC 3 or 4 blade with or without the assistance of Magill forceps as determined by the provider (17).

Control group: The NETT will be warmed in saline prior to use (18). Water-based lubrication will be applied on the nasotracheal RAE tube. The nasotracheal tube will be inserted into the nasal passage and advanced into the oropharynx. The nasotracheal tube will then be guided into the trachea past the vocal cords under direct visualization with CMAC video laryngoscope MAC 3 or 4 blade with or without the assistance of Magill forceps as determined by the provider.

Outcome Measures:

- Incidence of bleeding in posterior oropharynx
- Severity of bleeding in posterior oropharynx
- Need to suction the posterior oropharynx to facilitate intubation
- Time from first insertion of catheter or nasal RAE tube to ETCO₂
- Number of intubation attempts
- Recruitment of the other naris for intubation
- Use of Magill forceps to facilitate intubation
- Use of rescue technique (fiberoptic, oral intubation) to facilitate intubation
- Patient rating of nasal pain on side of intubation
- Anesthesiologist intervention outside of protocol
- Premature termination of procedure
- Unplanned hospital admission
- Unanticipated complications

4. Study Procedures:

- Identify and screen patients for study eligibility based on inclusion and exclusion criteria.
- Randomize subjects to the RRC or control group in a 1:1 ratio according to a computer-generated block randomization list (multi-center). (Research only)
- Administer premedication in the preoperative area (standard of care)
- Administer 1 spray of oxymetazoline per nostril in preoperative area (standard of care).
- Perform patency test in the preoperative area to determine which nares to use for initial attempt (standard of care).
- All standard monitoring (BP, EKG, and pulse oximeter) will be placed on all patients in the operating room (standard of care).
- Administer 1 spray of oxymetazoline per nostril prior to preoxygenation in the operating room (standard of care).
- Apply standard preoxygenation with full face mask (standard of care).
- Patients will undergo standardized NTI facilitated by RRC or direct insertion based on study group. Both procedures for nasal intubation are considered standard of care.
- Time from insertion of RRC or NETT into nasal passage to first recording of end-tidal CO₂ on monitor will be recorded (standard of care).
- Incidence and severity of epistaxis will be graded by a member of the anesthesia team according to a scale previously described and recorded (19, 20) (Research only).
- Anesthesia providers will record the number of intubation attempts, recruitment of the other naris, premature termination of the procedure, use of Magill forceps and use of rescue techniques to facilitate intubation, and other interventions, complications, or deviations from protocol during intubation in the EMR using a quick note.
- Postoperatively patients will be asked to rate their level of nasal pain on the side (left or right) that NTI was performed using a numerical rating scale at 30 and 60 minutes post emergence from anesthesia. Pain will be evaluated with Numeric Rating Scale (0=no pain and 10- worst pain imaginable). (Research only).

5. Sub-Study Procedures:

- N/A

6. Criteria for Inclusion of Subjects:

- Age > 18, male and female
- Subjects undergoing surgery requiring NTI
- ASA 1-3

7. Criteria for Exclusion of Subjects:

- History of anticoagulant use or coagulopathy
- History of latex allergy
- History of difficult airway
- Anticipated difficult airway requiring awake intubation
- Abnormal anatomy of the nasal passage (due to prior trauma, surgery, congenital defects, etc.) or basilar skull fracture
- Patients unable to be placed in the sniffing position

- Morbid obesity with BMI > 40
- Pregnancy
- ASA 4

8. Sources of Research Material:

- Subjects undergoing surgery requiring NTI
- Electronic Medical Record
- Anesthesia Reports
- PHI including name, medical record number, contact information including demographic information including age, gender, race, birth date, weight, height, BMI and medical and surgical history, medication list, ASA classification.
- **Procedural intubation-related variables:** incidence and severity of epistaxis, time from beginning intubation (insertion of nasopharyngeal airway or NETT into nasal passage) to ETCO₂, subjective pain rating using validated scale, number of attempts, whether the provider had to attempt on the other naris, use of Magill forceps to facilitate endotracheal intubation, use of rescue techniques to facilitate intubation, and any anesthesiologist modifications, interventions, or deviations from protocol necessary to successfully intubate or address complications (i.e., suctioning, insertion of an oral/nasal airway, conversion to oral endotracheal intubation, change in tube size etc.).
- Modified Cormack-Lehane classification: Grade 1-full view of glottis; Grade 2a-Partial view of glottis; 2b-Only posterior view of glottis; Grade 3-Only epiglottis seen, none of glottis seen; Grade 4- Neither glottis, nor epiglottis seen.
- C MAC Laryngoscope blade type (3 or 4)
- **Biometric variables:** oxygen saturation (baseline) and the lowest SpO₂ during intubation
Duration of anesthesia and procedure
- **Postoperative Recovery:** time spent in PACU, pain score at 30 and 60 minutes, unanticipated complications and hospital admissions.

9. Recruitment Methods and Consenting Process:

Subjects will be identified for potential eligibility by reviewing the weekly main operating room surgery schedule. Eligible subjects will be patients of the PI, co-investigators or other anesthesiologists. Other anesthesiologists will be contacted verbally or by email 1 day prior to the scheduled surgery for their permission to enroll the subjects. A "Dear Doctor Letter" will be sent to physicians via email. Without the confirmation of their consent, investigators will not enroll the subjects.

A designated team of study personnel will be responsible for screening, consenting and enrolling potential subjects. Consenting and enrollment will take place in the preoperative holding area. Information about the study will be given in a pressure-free, confidential private area in a face-to-face meeting and the voluntary nature of the research will be emphasized to the subjects.

The purpose of the study will be explained to the subject. Potential risks and complications will be reviewed. Adequate time will be given for the subject to consider whether to participate in the

study and all questions will be answered by a member of the study team. If the subject agrees to participate, then he or she will sign the consent form and HIPAA Authorization Form prior to any study procedures. In the case of Spanish-only speaking subjects, a live interpreter will be utilized for the above process and the consent and HIPAA Authorization Form will be provided to the subject in Spanish. Subjects will receive a copy of the signed documents.

10. Potential Risks:

This study has minimal risk. The anesthetic management in each group will not differ from the current standard of care.

Risk for RRC: There may be risk for mucosal injury and bleeding with RRC-guided NTI. This risk is not anticipated to be higher than for standard NTI in adults.

Psychological Stress: Some of the questions related to the study may make the subject feel uncomfortable. Subjects may refuse to answer any of the questions, take a break, or stop participation in the study at any time.

Loss of Confidentiality: Any time information is collected; there is a potential risk of loss of confidentiality. Every effort will be made to keep your information confidential.

11. Subject Safety and Data Monitoring:

Investigators will ensure patient safety throughout the procedure. This will include following all standards of care with regard to conducting a safe anesthetic and intubation in the operating room. All standard ASA monitors will be used and proper interventions by the providers will be carried out for complications or difficult intubation. Subjects will recover from the anesthetic in the post-anesthesia care unit. All data will be collected by the anesthesia providers and study personnel.

Data and Safety monitoring plan includes the formation of a Data and Safety Monitoring Board (DSMB). As independent research expert, Board Certified Anesthesiologists [name] and [name] will review safety and data information. The DSMB will also obtain the results of the interim analysis after 50% enrollment.

12. Procedures to Maintain Confidentiality:

All participants will be given an identification number such that identifiable, personal information will not be used. There will be link to MR number. Subjects will be identified to collect data and verify the data. Every effort will be made to keep all data collection sheets confidential and any electronic data sets will be password protected and secure. Electronic documents will be de-identified according to information security policies. Paper documents will be shredded.

13. Potential Benefits:

There is no benefit to subjects. Use of the RRC may lead to a significant decrease in epistaxis and pain in patients undergoing NTI. Information gained from this study will potentially improve future outcomes in this patient population through reducing complications of nasotracheal intubation.

14. Data Sharing;

MD Anderson site will provide deidentified protocol requiring data via REDCap. UT Southwestern team who have access to MD Anderson Center RedCap will download the de-identified data. REDCap (<https://redcap.mdanderson.org>) is hosted on a secure server by MD Anderson Cancer Center's Department of Oncology Care & Research Information Systems. REDCap has undergone an annual Governance Risk & Compliance Assessment (since May 2014) by MD Anderson's Information Security Office and found to be compliant with HIPAA, Texas Administrative Codes 202-203, University of Texas Policy 165, federal regulations outlined in 21CFR Part 11, and UTMDACC Institutional Policy #ADM0335.

Those having access to the data include the study PI's and research team personnel of both study sites. Users are authenticated against MDACC's Active Directory system. External collaborators are given access to the database once approved by the PI, with their access expiring in 6 months, but renewable in 6 months increments at the request of the PI. The application is accessed through Secure Socket Layer (SSL).

15. Biostatistics: (omit this section for peer-reviewed research such as cooperative group, or NIH- sponsored studies, and for industry-sponsored research which has been submitted to FDA)

Assuming the incidence of bleeding to be 50% and 24% in the control and RRC group, respectively, a sample size of 53 subjects per group (total n=106) are needed. This study is designed to have 80% power with alpha = 5%, two-sided. Assuming a dropout of 5%, a total of 112 subjects (56 in each arm) are required for this study. The sample size calculation was based on the chisquare tests.

Baseline characteristics (Demographics, Comorbidities) of all randomized patients will be summarized and presented in tables. Categorical variables will be presented as proportions and continuous variables as mean (SD) or median (range) as appropriate. The baseline differences between the two treatment arms will be assessed by Chi square/Fisher exact tests for proportions and Student t-test/Wilcoxon ranksum test for continuous variables as appropriate.

An intention to treat analysis will be conducted to assess the primary endpoint of bleeding. Logistic regression analysis will be conducted to model the primary endpoint between the treatment groups accounting for other confounders. Individual logistic regressions analyses will be conducted to model the secondary outcomes adjusting for treatment groups and other confounders. A univariate and a multivariable linear regression analysis will be conducted for those secondary outcomes, which are measured as continuous variables. A per protocol analysis will also be conducted where

patients with protocol violations will be excluded from the analysis. All analyses will be done using SAS 9.4 and $p < 0.05$ will be considered statistically significant.

15. References:

1. Chauhan, V. and Acharya, G. (2016) Nasal Intubation: A Comprehensive Review. *Indian Journal of Critical Care Medicine*, 20,662-667. doi:10.4103/0972-5229.194013
2. Hall, C.E. and Shutt, L.E. (2003) Nasotracheal Intubation for Head and Neck Surgery. *Anaesthesia*, 58, 249-256. doi:10.1046/j.1365-2044.2003.03034.x
4. Prasanna, D. and Bhat, S. (2014) Nasotracheal intubation: an overview. *Journal of Maxillofacial and Oral Surgery*, 13, 366-372. doi:10.1007/s12663-013-0516-5

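### Does the per-protocol analysis remove the severe bleeds, because suction and oral conversion are recorded alongside protocol deviations?

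*Combined protocol and SAP*

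**What the plan says.** Four parts of the combined protocol and SAP bear on this.

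- **Section 3, bleeding scale.** Five minutes after intubation, "a non-collaborating anesthesia provider blinded to the method of intubation will grade the severity of bleeding". The severe grade, however, refers to events during intubation, before that assessor arrives: "a large amount of blood in the pharynx impeding nasotracheal intubation—before the epistaxis assessor enters the" theatre. Such a bleed is described as "requiring suction for intubation or necessitating urgent orotracheal intubation".
- **Section 3, Outcome Measures.** The need for suction and the use of a rescue technique, with oral intubation named, are each listed as outcomes. A separate line reads "Anesthesiologist intervention outside of protocol".
- **Sections 4 and 8, data collected.** In Section 4, providers record attempts, Magill forceps and rescue techniques, and then "other interventions, complications, or deviations from protocol during intubation in the EMR using a quick note". In Section 8, the list of intubation variables ends with modifications by the anesthesiologist, together with "interventions, or deviations from protocol necessary to successfully intubate or address complications (i.e., suctioning, insertion of an oral/nasal airway, conversion to oral endotracheal intubation" and change in tube size.
- **Section 15, analysis.** The primary endpoint is analysed by intention to treat. A per-protocol analysis is added, in which "patients with protocol violations will be excluded from the analysis". Neither violation nor deviation is defined.

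**The concern.** Suction and urgent oral intubation mark a bleed as severe. They are also two of the four examples that Section 8 gives under a heading that includes deviations from protocol, and Section 8 holds the only itemised list of departures in the document. If an analyst used that list to decide who counts as a violator under Section 15, a severe bleed would be both an endpoint event and a reason to drop the patient.

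That would be a post-randomisation exclusion on the outcome, based on acts performed and recorded by staff who know the arm. The severe grade would be empty in the per-protocol set. The protocol expects that "RRC-guided NTI will be associated with significant lower incidence and severity of epistaxis in adult patients", so more control patients than RRC patients could be lost. The per-protocol result could then disagree with the intention-to-treat result for reasons of definition alone. An exclusion rule left undefined can also be settled after outcomes are known.

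**Working it through.** **1. The plan's own figure.** Section 15 gives 50% against 24% bleeding, two-sided 5%, 80% power and a chi-square test. With pooled variance under the null and mean rate 0.37:

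n = [1.960·√(2·0.37·0.63) + 0.842·√(0.50·0.50 + 0.24·0.76)]² / 0.26² = 52.9, so 53 per arm.

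Allowing for dropout, 106/0.95 = 111.6, so 112. Both figures reproduce. The planned odds ratio is (0.24/0.76)/(0.50/0.50) = 0.316.

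**2. Does the text make these acts violations?**

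| Place | Treatment of suction and oral conversion |
|---|---|
| Section 3, bleeding scale | Part of the definition of severe |
| Section 3, Outcome Measures | Outcomes, listed apart from off-protocol intervention |
| Section 4 | Rescue techniques named before other interventions and deviations |
| Section 8 | Examples under a joint heading of modifications, interventions or deviations |
| Section 11 | Providers are to intervene for complications or difficult intubation |
| Section 15 | Excludes violations, without naming these acts or pointing to Section 8 |

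Section 8 is a data-collection list with a three-part heading, and suctioning fits the word interventions at least as well as deviations. No stated rule links it to Section 15.

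**3. Size if the exclusion were applied.** The documents give no severe-bleed rate, so the severe rates s below are assumptions. With bleeding rate p, removing severe cases leaves:

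- rate (p − s)/(1 − s)
- odds (p − s)/(1 − p)

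The odds ratio is therefore multiplied by (1 − s_R/p_R)/(1 − s_C/p_C). It moves only if severe bleeds are a different share of bleeders in the two arms. For 10%/2%, the control odds are 0.40/0.50 = 0.800 and the RRC odds 0.22/0.76 = 0.289, so the odds ratio is 0.362.

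Power is by exact enumeration of the Pearson chi-square test, 53 per arm before exclusion, with the number of severe cases binomial in each arm.

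| Severe, control/RRC | Per-protocol rates | Difference (points) | Odds ratio | Power |
|---|---|---|---|---|
| none removed | 50.0% / 24.0% | 26.0 | 0.316 | 0.811 |
| 2% / 1% | 49.0% / 23.2% | 25.7 | 0.315 | 0.796 |
| 5% / 1% | 47.4% / 23.2% | 24.1 | 0.336 | 0.740 |
| 10% / 2% | 44.4% / 22.4% | 22.0 | 0.362 | 0.656 |
| 15% / 3% | 41.2% / 21.6% | 19.5 | 0.395 | 0.553 |
| 10% / 4.8% (equal share of bleeders) | 44.4% / 20.2% | 24.3 | 0.316 | 0.745 |

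The 15% row makes 0.15/0.50 = 30% of control bleeders severe, which nothing in the documents supports.

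**4. Equal true incidence.** With 50% bleeding in both arms and severe rates 10%/2%, the per-protocol rates are 44.4% control and 49.0% RRC. That is 4.5 points against RRC, an odds ratio of 0.96/0.80 = 1.20. The chance of a significant result against RRC is about 7%; with no exclusion, the same calculation gives about 2%.

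**The case for a change.** The strongest case for a change is that Sections 3 and 8 point in different directions and Section 15 does not say which governs. Both acts are named in Section 8, the list does not separate interventions from deviations, and an analyst working from it literally could empty the severe grade. The comparison of severity would lose its top category whatever the rate. A sentence or two would settle the matter without touching any procedure.

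Much of this stands. The exclusionary reading is possible, the arithmetic behind it is right, and a written definition of violation would be tidier. What does not stand is the step from possible to planned. The outcome list treats suction and oral rescue as things to be compared between arms, and Section 11 expects providers to intervene when complications arise. Reading such acts as violations would set the per-protocol analysis against the trial's own outcome list.

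The stated direction of bias also needs a condition. More severe cases in control are not enough to move the odds ratio, which is the effect measure of the planned logistic regression. Severe bleeds must be a larger share of control bleeders. In the equal-share row power falls because patients are lost, while the odds ratio stays at 0.316.

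One possible addition would be to take the severe grade from suction or conversion entries where blood was the reason. That is less simple than it sounds, because Sections 3, 4 and 8 do not require a reason to be recorded.

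**Conclusion.** No change to the plan follows. Section 15 leaves protocol violation undefined, but no rule in the document makes suction or oral conversion a violation. A competent analyst would base the per-protocol set on eligibility and use of the assigned technique, and would not exclude patients for events that the protocol lists as outcomes.

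Even on the exclusionary reading, the harm is confined to a supportive analysis. At the planned 50% and 24%, and over assumed severe rates from 2%/1% to 15%/3%, the odds ratio would lie between 0.315 and 0.395 against 0.316, always in favour of RRC. Power in the per-protocol set would fall to between 0.796 and 0.553, but the trial is not sized on that set. The severe grade would be empty there, which matters for a per-protocol comparison of severity and for nothing else.

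The intention-to-treat analysis of bleeding and the sample size of 112 are unaffected. These sizes rest wholly on assumed severe rates. The conclusion itself rests on the wording of Sections 3, 8, 11 and 15, not on those rates.
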